7.1 Risks and Burdens to Participants

Work Package 2 - Due to the nature of the intervention, we do not anticipate any unwanted incidents, adverse events or effects on our participants. Nevertheless, we will have procedures in place for reporting of adverse events or serious adverse events, as detailed in the safety reporting section.

There is a risk of reaction to the tape used in the intervention. Participants will be asked in the PIS and again prior to consent if they have a known allergy to any form of adhesive taping. They will be excluded if they declare any known allergies to the tape.

We will also ensure that participants with fragile skin or with thin, easily bruised skin will not take part. Despite these precautions, if a participant develops skin irritation, however minor, we will withdraw them from the trial and will advise them to see their GP.

There is a risk that participants may see no improvement or worsening of symptoms following taping intervention, if this happens, we will refer them back to their GP or referring clinician at the end of the study when it is clear the intervention has not had an effect or has made any pain worse.

There is a time burden to this study, recruitment (including consent), taping demonstration, questionnaire completion. The feedback from our PPIE workshops was that the burden of time for visits and practically applying the tape was minimal, this was also outweighed by the benefits felt from wearing the tape.

Work Package 3: It is not anticipated that there are any risks to taking part in this study. However, there is a possibility that the participant may find discussing their experiences of the taping or knee pain upsetting. If this happens, we will ask them to please let the researcher know; they can take a break at any time or stop the interview if they wish to do so. If during the interview they reveal that their safety or the safety of others may be at risk, this information will be discussed with individuals outside the study team. This will be in the PIS and consent form to ensure full understanding.

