3.2 Outcome Measures

Primary outcome

 WP2: To assess recruitment to the study and retention: Participant uptake – number of participants recruited and number of participants who complete the study.

WP3: Report on participant experiences of taping and the trial process. Explore facilitators and barriers to adherence. Evaluate the performance of the participant treatment package.

Secondary outcomes (ii - vii)

- ii) To determine whether the tape can be applied by participants correctly at home: Clinical checks at 2 weeks recorded on the Clinical Report Form.
- iii) Adherence:
 - a. Number of returned or counted unused tapes
 - b. Number of days since the previous timepoint that participants report wearing the tape collected at weeks 2, 6 and 12.
 - c. Average number of hours the participants report wearing the tape daily since the previous timepoint at weeks 2, 6 and 12.
- (iv & v) To assess how to optimise adherence of taping over an extended period and to determine participants views about the acceptability of prolonged taping: Participants interviews in WP3.
- (vi) Effect of intervention: Reduction in pain

- (a) Knee pain measured by VAS_{NA} at baseline, 2, 6 & 12 weeks.
- (b) Knee pain and function measured by KOOS-PF at baseline, 2, 6 & 12 weeks.
- (vii) To determine a primary outcome for a large scale RCT and to inform sample size calculation: Analysis of quantitative data in vi a & b

4. Study Design and Methods of Data Collection

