Participants will be assessed face-to-face at baseline and again face-to-face after 2 weeks and then by telephone or online (e.g. Zoom, Teams) at 6 and 12 weeks. At baseline and weeks 2, 6 and 12 subjects will complete the following assessments: Knee pain during a nominated aggravating activity (VAS_{NA} 0-10), the Knee Osteoarthritis & Injury Outcome Score for the patellofemoral joint (KOOS-PF) (20). Subjects will have a face-to-face assessment 2 weeks after treatment commences to check for correct application of the tape. At this 2 week visit a further 10 weeks of tape will be supplied. At each contact, participants will be asked about treatment adherence. They will be asked since the last timepoint (Baseline, or weeks 2, 6 or 12) approximately how many days per week and how many hours per day on average the tape was worn.

As there is no gold standard for measuring adherence to taping, we will estimate adherence by counting the number of unused strips of tape at the end of the trial and by asking how many days per week and how many hours per day on average the tape was worn. We will collect this information at the 2 weeks tape check and at the two telephone or online consultations at 6 and 12 weeks. Participants will be encouraged to adhere to the tape during the 6-week telephone call. Information on any adverse events will also be collected at each contact.

Work Package 3 (WP3):

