Participants completing WP2 will all be given a PIS for WP3 and asked if they are interested in taking part in WP3. It will be explained that they may not be picked, depending on how many say yes as we will only require fifteen. Fifteen participants from the feasibility trial (WP2) will be invited to participate in one-to-one semi-structured interviews for WP3. Participants will be purposively recruited from those who consented to be contacted in WP2, to reflect a range of sex, age and ethnicity. It is anticipated that this sample size will be sufficient to generate rich data. However, recruitment will continue until data saturation has been achieved. Moreover, if data saturation is achieved before recruiting the fifteenth participant, recruitment will be stopped at that point. Purposive recruitment will allow us to include the voices of participants not commonly heard in this type of research, including those from underserved communities. As such, we are confident that purposively recruiting 15 participants is appropriate for this study. Semistructured interviews of approximately 60 minutes will be conducted to gain in-depth understanding of participants' experience of the intervention. Interviews will be informed by an interview guide developed from the findings of WP1, the research team including PPIE representative, underpinned by the Theoretical Framework of Acceptability (21) (see appendix 1). Participants will be interviewed by the research associate (RA) who is trained in undertaking qualitative interviews either in-person, online via Teams, or over the phone depending on the participants' preference. In-person interviews will take place in a private room at the [name], Manchester Metropolitan University. Two participants who will have taken part in the clinical trial will pilot the guide to ensure its appropriateness. Consent and demographic information will be collected at the start of the interview. Further discussion will be guided by each participant's response to the questions to allow exploration of unanticipated issues. Emerging findings from each interview will iteratively feed into subsequent interviews. Interviews will be digitally recorded, and interviews will be professionally transcribed.

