5.2 Study Setting and Sample Identification

Participants will be identified by [name] and clinical team at the Manchester Local Care Organisation (MLCO) or by [name] in clinics at Salford Royal Hospital. Participants will be given a PIS to read and consider.

Those who are interested in taking part will be invited to attend a face-to-face baseline visit at the NIHR Manchester Clinical Research Facility. At the baseline visit potential participants will be asked to confirm that they have received and read this PIS. The researcher will further discuss the study with the potential participant and give an opportunity for them to ask questions.

If recruitment is not met by the above clinics an advert will be posted on the University of Manchester intranet and in the Manchester Evening News. This will invite potential participants to scan a QR code which leads them to some basic questions about their knee health and skin condition. If they are suitable, they will be given details to contact the research team.

The assessment and delivery of WP2 will take place in the NIHR Manchester Clinical Research facility. Participants will self-apply the taping intervention in their homes. The delivery of WP3 will take place in the Department of Health Professions at [name], Manchester Metropolitan University. Participants will be purposefully selected from those in the WP2 arm who have completed the 12 weeks programme by the CI and [name] from the Manchester Metropolitan University.

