5.5 Consent

Subjects will be asked to sign an informed consent form in the presence of the CI prior to taking part in any study procedures. As part of the informed consent process, participants will have been given a PIS to read for at least 24 hours. At the baseline visit, participants will have the opportunity to ask any questions, discuss the research and their involvement before they decide.

At the last visit of WP2, participants will be asked if they would like information to take part in follow-up interviews to explore their experiences of the trial and intervention acceptability in WP3. Further PIS for WP3 will be provided at this stage.

WP3 may take place purely online (via Teams) or by telephone, therefore copies of the consent form will be sent and returned with scanned or e-signatures via email or through the post in pre-paid envelopes.

Data protection and confidentiality measures taken by the CI and the host institution will be explained to the participant.

It will also be explained that participants are free to withdraw consent at any time without giving any reason, and without their legal rights being affected. All data collated up to the point of withdrawal will be retained for use with the analysis.

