6.1 Data Analysis

Intervention arm WP2:

All variables will be examined using appropriate descriptive statistics (mean [standard deviation], median [interquartile range], n [%]) and graphics for completeness and form. No imputation will be made for missing data, however quantities and location will be used to inform the design of a future RCT.

The primary outcome, recruitment rate, will be presented as a proportion with 95% binomial confidence intervals. This will also be presented on a monthly basis. Other feasibility parameters, dropout rates and those with complete data, will be presented similarly.

Adherence, i.e. number of returned tapes and the number of days and average hours of daily usage, will be reported for each timepoint as continuous measures with mean/median and SD/IQR as appropriate. Overall measures of usage will be presented and comparative statistics or line graphs will illustrate any changes in usage over the study duration. It is possible there may be reasons other than non-adherence which result in unused tapes (e.g. major increases or decreases in symptoms). We will collect this information at the 2 weeks clinical check, at the two telephone consultations at 6 and 12 weeks, and during the qualitative study WP3. Further prompts to encourage tape adherence will be done during the telephone consultations using the questionnaires at 6 and 12 weeks.

Adverse events (such as skin irritation, the development of new pain in other body regions thought to be related to the interventions) will be presented as the total number and proportion.

The measures of treatment efficacy, pain scale (VAS_{NA} 0-10) and the Knee Osteoarthritis & Injury Outcome Score for the patellofemoral joint (KOOS-PF) (20) will be reported with descriptive statistics and graphics at baseline, 2, 6 and 12 weeks. Preliminary analysis of all timepoints alongside the change from baseline to 12 weeks will be presented to inform the design of the future full RCT. The KOOS-PF will be scored as per validated instructions (20). This includes a "rule" that a subscale score can be calculated if 50% or more of the items in specific subscale have been completed by the participant.

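### Any skin irritation, however minor, ends trial participation and not only taping, so remaining assessments and the WP3 interview are lost although most could still be obtained by telephone

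*Protocol*

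**What the plan says.** Section 7.1 (Risks and Burdens to Participants) states that "if a participant develops skin irritation, however minor, we will withdraw them from the trial and will advise them to see their GP". The same section treats participants with no improvement or worse symptoms differently: they are referred back to their GP or clinician only once the study ends.

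Under section 4.2, VAS and KOOS-PF are taken at baseline and at weeks 2, 6 and 12. Week 2 is face-to-face, and the last two are held "by telephone or online (e.g. Zoom, Teams) at 6 and 12 weeks". On safety, "Information on any adverse events will also be collected at each contact".

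On data after withdrawal, section 5.5 (Consent) says "All data collated up to the point of withdrawal will be retained for use with the analysis". Section 6.1 says "No imputation will be made for missing data" and presents the baseline-to-week-12 change to inform the future RCT.

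The retention part of the primary outcome in section 3.2 is the "number of participants who complete the study".

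For the interviews, section 4.2 says "Participants completing WP2 will all be given a PIS for WP3", and section 5.2 selects interviewees from those "who have completed the 12 weeks programme".

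**The concern.** Stopping the tape after a skin reaction is a reasonable safety step and is not in question. The difficulty is that the protocol makes stopping the tape and leaving the study a single event. Asking someone about knee pain by telephone needs no tape, so the data given up are largely obtainable.

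Three things are at stake:

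- **Retention.** It belongs to the primary objective in section 3.1, and the rule mixes exits imposed by the investigator with participants' own drop-out.
- **12-week outcomes.** The change scores meant to inform the RCT are missing for anyone withdrawn before week 12, and they are not imputed.
- **WP3.** The interviews explore barriers to adherence, yet people for whom the tape itself was the barrier do not reach the interview.

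A SAP could not repair this, because it cannot recover data that were never collected.

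**Working it through.** The plan gives no figure on this point. Its one computed interval, in section 5.3.1, concerns uptake and has no bearing here.

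**Inputs from the protocol.** Planned N = 30 (section 5.3.1). Post-baseline assessments at weeks 2, 6 and 12 (sections 4.2 and 4.4). Progression rows in section 4.2: loss to follow-up is Go below 10%, Edit from 10% to 20%, Stop above 20%; complete data is Go at 70% or more.

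**Step 1: does any section separate stopping tape from leaving the study?** Section 7.1 refers to the trial. Section 5.5 says what happens to data already held and schedules nothing later. Section 8 follows events to resolution, but within the process for serious adverse events, and it does not supply VAS or KOOS-PF. No other section does so.

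**Step 2: assessments lost, by time of report.** This assumes that the assessment at the contact where irritation is reported is still completed.

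| Irritation first reported | Later assessments lost, of 3 |
|---|---|
| Before week 2 | up to 3 (weeks 2, 6, 12) |
| At week 2 | 2 (weeks 6, 12) |
| At week 6 | 1 (week 12) |
| At week 12 | 0 |

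**Step 3: completion count.** Completion = (30 − w)/30, where w is the number withdrawn for irritation before week 12, with no other loss. Each withdrawal costs 1/30 = 3.3 points. Intervals are exact (Clopper-Pearson).

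| w | Completion | 95% CI |
|---|---|---|
| 1 | 29/30 = 96.7% | 82.8 to 99.9% |
| 2 | 28/30 = 93.3% | 77.9 to 99.2% |
| 3 | 27/30 = 90.0% | 73.5 to 97.9% |

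**Step 4: progression rows.** Suppose these withdrawals count as lost to follow-up and nothing else is lost. Then 2/30 = 6.7% stays in Go, 3/30 = 10.0% moves to Edit, and 7/30 = 23.3% is Stop. If they do not count there, that row is unaffected. The complete-data row needs 0.70 × 30 = 21 participants for Go and so tolerates 9 incomplete; it is unlikely to change from this cause alone.

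The irritation rate is not given. As an illustration only, let X be binomial (30, p), with every case withdrawn before week 12, all counted as lost and no other loss. P(Go) = P(X ≤ 2) is then 0.81 at p = 5%, 0.41 at 10%, 0.04 at 20% and 0.002 at 30%. These rates are assumptions without support in the protocol, and the conclusion does not rest on them.

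**Step 5: WP3.** Section 4.2 gives WP3 information to those completing WP2, section 5.2 requires completion of the 12-week programme, and the schedule in section 4.4 places the WP3 discussion at week 12. Someone withdrawn earlier meets none of these. The interview itself can be held by phone or online, so nothing practical stands in the way.

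**The case against.** The strongest reply is that this is one sentence in a risk section, written to reassure on safety, and that it may be loose wording for stopping the tape. The study is single-arm, descriptive and small, with no treatment contrast to protect. The tape is hypoallergenic, people with tape allergy or sensitive skin are excluded, and a 20% drop-out is already allowed for. Counting people who cannot tolerate tape as drop-outs could also be called a conservative reading of feasibility, and off-tape scores blur the objective about pain in response to tape.

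Part of this stands. The number affected may be small. Off-tape scores are a real drawback, which is why they should be flagged. Section 6.1 also names recruitment rate as the primary outcome and lists drop-out among other feasibility parameters, although sections 3.1 and 3.2 place retention or completion under the primary heading. But if the sentence is only loose wording, correcting it costs almost nothing. Tape intolerance is also shown more clearly when reported under its own name than when merged with drop-out.

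A reader might infer more than the documents support:

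- **That section 5.5 forbids later data collection.** It does not. Its sentence follows the right to withdraw consent, protects data already held, and does not say that only those data may be used.
- **That the irritation signal is lost.** Adverse events are asked about at each contact, and section 6.1 reports them as number and proportion, with skin irritation as an example. What is lost is the later scores and the interview.
- **That the WP3 exclusion comes from section 7.1 alone.** It comes from the completer wording in sections 4.2 and 5.2, which excludes every drop-out. Section 4.2 also speaks of recruiting from those who agreed in WP2 to be contacted, so the text is mixed, but section 5.2 requires completion.
- **That the pain and use-again rows are biased.** Both take all recruited participants as denominator, so this is not shown.

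**Conclusion.** The point holds as a design choice worth changing; it does not threaten the study's validity. Followed as written, section 7.1 gives up between none and all three of the post-baseline assessments, depending on when irritation is reported. It takes 3.3 points off completion for each withdrawal before week 12, and together with sections 4.2 and 5.2 it keeps these participants out of WP3. For cases reported before week 12 these consequences do not depend on how common irritation is. The 3.3 points assume that 30 are recruited.

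It would go too far to say that the rule will cost the study its Go decision. A shift from Go to Edit on loss to follow-up needs at least three such withdrawals if nothing else is lost, and it needs them to be counted in that row. The protocol settles neither the irritation rate nor the counting rule.

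**What to change.** - **Section 7.1:** replace withdrawal from the trial with stopping the tape, leaving the GP advice unchanged. State that, unless they withdraw consent, these participants are invited to their remaining scheduled assessments, including a question on whether the irritation resolved.
- **Sections 4.2 and 5.2:** amend the WP3 wording so that those who stopped tape are eligible for interview. Editing section 7.1 alone would not achieve this.
- **Section 6.1 and the progression table:** report tape discontinuations separately from drop-outs, say whether they count as lost to follow-up, and flag 12-week scores taken off tape.

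The cost is small wording changes to the protocol and PIS. The week 6 and 12 contacts are already scheduled and remote, and there is no added tape exposure. The downside is that some 12-week scores will be off tape; flagging them allows the pain results to be shown with and without them.

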7.2 Research Ethics Committee (REC) and Other Regulatory Review & Reports

Before the start of the study, a favourable opinion will be sought from a REC and/ or HRA depending on the type of study for the study protocol, informed consent forms and other relevant participant facing documents e.g., advertisements.

7.2.1 NHS REC Reviewed Research

Before the start of the study, a favourable opinion will be sought from an NHS Research Ethics Committee (REC) for the study and all the supporting documents including the protocol, information sheets, informed consent forms and other relevant documents. The Protocol FINAL v. 1.0 Date: 02/Oct/2024 IRAS ID: 322953

study team will be responsible for the maintenance of a trial master file or TMF, in which all current and superseded study documents will be retained. Also contained in the site file/TMF will be the approval documentation including correspondence with relevant authorities such as the HRA and REC.

The Chief Investigator will notify the REC of the end of the study, and will submit a final report with the results, including any publications/abstracts, to the REC within 12 months of the end of the study. If the study is ended prematurely, the Chief Investigator will notify the REC, including the reasons for the premature termination.

No participants will be enrolled into this research study prior to the study being reviewed by the relevant regulatory authorities and receiving HRA and REC approvals, as well as approval from the R&D office at Manchester University NHS Foundation Trust.

7.3 Amendments

7.3.1 Studies Involving the NHS

Any amendments to the study shall be reviewed by the Sponsorship Team prior to submission. Any non-substantial amendments shall be notified to the HRA and any substantial amendments, along with amended documentation, shall be approved by the REC, and HRA, prior to implementation as per nationally agreed guidelines. The Chief Investigator or designee will work with the R&I department to put the necessary arrangements in place to implement the amendment and to confirm their support for the study as amended.

7.4 Peer Review

This study has been peer reviewed by the NIHR as part of the grant process.

7.5 Patient & Public Involvement

To inform the original successful application for this grant, a group of five patients were gathered and the concept of the taping method and the project as a whole were discussed. The patients were very positive and enthusiastic about sports taping being used for painful PFJOA. Findings from this discussion assisted the design of the intervention phase. The relevance of the questions asked, and the acceptability of the reasoning were also confirmed.

To help us plan the first workshop, three people with a lived experience of kneecap arthritis took part in a Patient and Public Involvement and Engagement (PPIE) consultation meeting. The participants' age range was 40-59, two were female, two identified as White British, one as Asian/Kashmir. They helped us with participant recruitment, and the planning, content and running of WP1.

Prior to this current protocol, WP1 (mentioned in 4.1 of this protocol) was undertaken in January and February 2024. This involved two workshops. The purpose of these workshops was to co-design and refine a treatment package using patellar taping for kneecap arthritis, for use in a subsequent clinical trial feasibility study (WP2). In workshop 1, 11 participants with a lived experience of kneecap arthritis co-designed the intervention with regards to the resources (video and participant instructions) to be used in WP2. Participants age range was 50-81, 10 were female, six identified as white British, six Asian/British Asian, one Black/Black British; UK indices of deprivation deciles ranged from 2-9. The preliminary findings and prototype resources developed from workshop 1 were shared with the same participants in a follow-up workshop (workshop 2). The final resources and any amendments were discussed and agreed on. This work package (WP1) then fully informed WP2 methodology described below.

We also have a PPIE Co Applicant who has been involved from the start ([name], - [name]). She attends the TMG meetings and had full input in the design of the intervention methodology during the workshops in WP1. She helped prepare our forward-facing documents for WP1 and will support the development of participant facing documents in WP2 and WP3, support the data generation and analysis in WP3 and advise on dissemination plans at the later stages.

